9.2.2.2 Treatment Follow-up (C1 to C7 +, D1 to D127 +)

Treatment Visits (C1 to C7, D1 to D127)

Treatment visits will be performed on the first day of the first 7 treatment cycles (C1 to C7) (CnD1, n = 1 to 7), with the exception of C1D1, and two additional treatment visits will be added on C1D8 and C1D15, respectively. The specific visit procedures are as follows:

- The investigational product will be dosed once daily
- Full physical examination, body weight examination, ECOG PS score, vital signs, laboratory tests (clinical chemistry, hematology, and urinalysis), and 12-lead ECG will be performed every 3 weeks (CnD1)
- Two additional tests will be added on C1D8 and C1D15: including vital signs, laboratory tests (clinical chemistry, hematology, and urinalysis), and 12-lead ECG
- Ophthalmic examinations will be performed as clinically indicated throughout the treatment period, and the specific items will be determined by the investigator or specialist depending on the patient's condition
- Echocardiography will be performed on C1D1 and every 12 weeks (and as clinically indicated)
- Tumor assessments per RECIST 1.1 will be recommended to be performed every 6 weeks

- The adverse events and concomitant medications will be recorded

Treatment Visits (C7 +, D127 +)

Treatment visits after Cycle 7 will be performed according to the following procedures:

- The investigational product will be dosed once daily
- Full physical examination, body weight examination, ECOG PS score, vital signs, clinical chemistry, hematology, urinalysis, and 12-lead ECG will be performed every 6 weeks
- Ophthalmic examinations will be performed as clinically indicated, and the specific items will be determined by the investigator or specialist depending on the patient's condition
- Echocardiography will be performed every 12 weeks (and as clinically indicated) from the first dose of HS-10296
- Tumor assessments per RECIST 1.1 will be recommended to be performed every 6 weeks
- The adverse events and concomitant medications will be recorded

9.2.2.3 Study Discontinuation Follow-up

Subjects who receive HS-10296 crossover treatment should discontinue HS-10296 when they meet withdrawal criteria or discontinuation criteria, and discontinuation follow-up will be required at the time of discontinuation. It includes the following items:

- Full physical examination, body weight examination, ECOG PS score, vital signs, laboratory tests (clinical chemistry, hematology, and urinalysis), 12-lead ECG, and echocardiography
- Record anti-tumor therapy
- If a subject has disease progression during the crossover treatment period, tumor and/or blood samples will be collected (optional) based on the subject's willingness for post-disease progression genetic testing so as to guide further treatments
- Record adverse events

During the discontinuation visit, repeated examinations will not be required if the results of the safety tests (full physical examination, body weight examination, ECOG PS score, vital signs, laboratory tests, and 12-lead ECG) within the previous 7 days are available; and repeated examinations will also not be required if the results of the RECIST response evaluations and echocardiography within the previous 4 weeks are available.

9.2.2.4 Safety Follow-up

A 28-day safety follow-up will be performed after discontinuation of HS-10296 crossover treatment (discontinuation of the investigational product) to record AEs, SAEs, and concomitant medications. If there are abnormal and clinically significant changes, the abnormal

condition should be followed up until recovery (to baseline, normal laboratory values, or abnormal values judged as clinically insignificant by the investigator) or stabilization.

- Record adverse events (newly emerged AEs or follow-up of AEs experienced at the time of discontinuation)
- Record concomitant medications (all concomitant medications including anti-tumor therapy)

9.2.2.5 Progression Follow-up

In the HS-10296 crossover treatment period, any patient who discontinues the HS-10296 crossover treatment for reasons other than objective disease progression should have a scheduled progression follow-up until disease progression as assessed by the investigator per RECIST 1.1, unless the patient withdraws the informed consent.

- Response evaluations in solid tumors will be performed every 6 weeks until disease progression as assessed by the Investigator per RECIST 1.1
- ECOG PS score will be performed every 6 weeks until disease progression as assessed by the investigator per RECIST 1.1
- Record concomitant medications: only subsequent anti-tumor therapy will be recorded in detail until disease progression
- If a subject has disease progression before the completion of the 28-day safety follow-up, the safety follow-up should be continued until 28 days after discontinuation of treatment

9.2.2.6 Survival Follow-up

- Perform follow-up every 6 weeks (relative to the date of disease progression at the time of crossover treatment) to record details of subsequent anti-tumor therapy
- Perform follow-up every 6 weeks (relative to the date of disease progression) to record subsequent response/progression data
- Perform follow-up every 6 weeks (relative to the date of disease progression) to record survival status

If the progression follow-up for crossover treatment is not completed according to the study procedures, and the date of disease progression is missing, the dates of documented refusal to progression follow-up for crossover treatment/acceptance of survival follow-up will be used as the starting point.

9.3 Unscheduled Visits/Examinations

The investigator may schedule unscheduled visits or examinations according to the subject's condition, especially if the subject experiences an AE. Unscheduled visits and unscheduled

examinations performed during that visit will be recorded in the eCRF, along with the reason for the unscheduled visit (or examination).

10.0 Study Assessments

10.1 Study Specific Steps

The following contents specify the detailed requirements and descriptions of each step in the study procedure and the indicators for examination/assessment.

10.1.1 Informed Consent Process

The informed consent form (ICF) must be obtained prior to subject enrollment and study procedures. The ICFs at enrollment should include the informed consent for participation in the study, for obtaining tumor tissue samples at screening, for blood sample collection, and for tumor samples collection at disease progression (optional).

After confirmation of disease progression by central review and unblinding, subjects in the gefitinib group should sign the ICF for HS-10296 crossover treatment, including the informed consent for participation in crossover treatment, for tumor samples collection after disease progression, and for blood samples collection. The ICF for crossover treatment will be signed as an independent ICF, separate from the ICF signed at enrollment.

10.1.2 Assignment of Screening Number

Each patient will be assigned a unique screening number at the time informed consent is obtained. Screening numbers for subjects who have failed the screening tests or have withdrawn from the study should not be reused.

10.1.3 Screening and Enrollment

Each enrolled subject shall provide the informed consent form prior to the initiation of any study procedures, after which screening tests will be performed to determine the subject's eligibility.

Tumor assessments and other clinical data obtained prior to the informed consent may be used for the study without re-examination if the time of assessment is within the timeframe specified in the protocol. The screening procedure is recommended to start with confirmation of EGFR mutation status by central laboratory test.

Tumor tissue samples collection for EGFR mutation status test at screening may not be limited to the 28-day timeframe, but samples must be collected after diagnosis of locally advanced or metastatic NSCLC.

Baseline CT or MRI assessment of chest, abdomen, and brain tissue (contrast CT/MRI is recommended) must be performed within 28 days prior to the start of study treatment

(regardless of the time of signing the ICF), and it should be performed as close as possible to the start of study treatment. If the only target lesion has undergone a diagnostic biopsy, a baseline assessment of tumor lesions should be performed at least 14 days later.

If laboratory tests (clinical chemistry, hematology, and urinalysis) are performed within 7 days prior to randomization, they may not need to be repeated at the first study treatment (C1D1) visit.

If a laboratory value at screening is abnormal, the test may be repeated once within 1 week, and the re-test results will be used as the basis for assessment of eligibility criteria. For subjects who are tested out of the timeframe or fail at screening, a second screening may be performed if the Investigator believes that they may be eligible for enrollment. Subjects who are re-screened need to re-sign the ICF and use a new screening number.

10.1.4 Assignment of Randomization Number

Subjects who are eligible for screening will be assigned a randomization number generated from the IWRS prior to the first dose of the investigational product (C1D1).

10.1.5 Data Collection

Demographic data and other characteristics, including date of birth or age, sex, race and smoking status of patients, will be collected at screening as per the study plan ([Appendix B](#)).

Complete medical history will be collected: including past and current medical history of kidney, liver, blood system, digestive tract, endocrine, immune, metabolic, cardiovascular, lung, and nervous systems, psychiatric disorders, infections and inflammatory diseases.

Treatment history: drug (chemotherapy, prescription drugs, over-the-counter drugs, other drugs) and non-drug therapies (surgery, radiotherapy, etc.) will be recorded.

Allergy history: the subject's history of allergy to drugs or other substances will be recorded.

10.1.6 Physical Examination

Physical examinations will be performed at screening, every 3 weeks for C1 to C7, every 6 weeks for C7 + cycles, and at the discontinuation follow-up as per the study plan ([Appendix B](#)).

Baseline physical examination (defined as assessments performed prior to the start of the investigational product) will include the following systems: 1) eyes; 2) ears, nose, throat; 3) cardiovascular system; 4) respiratory system; 5) gastrointestinal system; 6) skin; 7) extremities; 8) musculoskeletal system; 9) nervous system; 10) lymph nodes; 11) others. All routine physical examinations in each subsequent treatment cycle, with the exception of neurological examinations, should assess whether a significant change from baseline is clinically significant.

10.1.7 ECOG PS Score

ECOG PS scores will be performed at screening, every 3 weeks for C1 to C7, every 6 weeks for C7 + cycles, and at discontinuation follow-up and progression follow-up as per the study plan ([Appendix B](#)).

0=Fully active, able to carry on all pre-disease performance without restriction.

1 = Restricted in physically strenuous activity but ambulatory and able to carry out work of a light or sedentary nature, e.g., light house work, office work.

2 = Ambulatory and capable of all self-care but unable to carry out any work activities, up and about more than 50% of waking hours.

3 = capable of only limited self-care, confined to bed or chair more than 50% of waking hours.

4 = Bedridden, unable to take care of oneself.

5 = Death

10.1.8 Body Weight and Body Height Measurements

Height will be measured at screening as per the study plan ([Appendix B](#)); body weight will be measured at the same time as the physical examination. Subjects should wear indoor clothing and take off shoes when measuring body weight and height.

10.1.9 Vital Signs Measurement

Vital signs will be performed at screening, every 3 weeks for C1 to C7, every 6 weeks for C7 + cycles, on C1D8 and C1D15, and at discontinuation follow-up as per the study plan ([Appendix B](#)).

Vital sign measurements will be collected, including body temperature (oral or ear or axillary temperature in degrees Celsius), blood pressure (systolic and diastolic), pulse rate (heart rate per minute), and respiratory rate. Measure blood pressure and pulse after the patient has been sitting for at least 10 minutes. Additional tests may be performed if it is deemed necessary by the investigator as appropriate.

10.1.10 Laboratory Tests

Laboratory tests will be performed at screening, every 3 weeks for C1 to C7, every 6 weeks for C7 + cycles, on C1D8 and C1D15, and at discontinuation follow-up as per the study plan ([Appendix B](#)).

Additional tests may be performed if it is deemed necessary by the investigator as appropriate.

The values, units, and reference ranges of the test results should be recorded in the eCRF.

Laboratory results that reach CTCAE (4.0) Grade 3 or have a significant change from baseline and are considered to be of clinical interest will be reexamined/confirmed within 7 days and

followed up accordingly.

Laboratory test items are listed in Table 3.

Table 3 Laboratory Test Items

Clinical Chemistry	Hematology	Urinalysis
Serum (S)/Plasma (P)-albumin	Blood (B) -Hemoglobin	U-Glucose
S/P-ALT	B-White blood cells	U-Protein
S/P-AST	B-Hematocrit	U-Blood
S/P-Alkaline phosphatase	B-Red blood cell count (RBC)	
S/P-Bilirubin, Total bilirubin	B-Absolute differential white blood cell count	
S/P-Calcium, Total blood calcium	Neutrophils	
S/P-Creatinine	Lymphocytes	
S/P-Creatine kinase	Monocytes	
S/P-Glucose	Basophils	
S/P-LDH	Eosinophils	
S/P-HbA1C	B-Platelet count	
S/P-Magnesium	B-Reticulocytes	
S/P-Potassium		
S/P-Sodium		
S/P-Urea nitrogen or urea (either)		

If AST or ALT $\geq 3 \times$ ULN and total bilirubin $\geq 2 \times$ ULN, please refer to [Appendix C](#) (Hy's law) for further guidance for actions to be taken in the event of combined increases in aminotransferases and total bilirubin.

10.1.11 Electrocardiogram

12-lead ECGs will be performed at screening, every 3 weeks for C1 to C7, every 6 weeks for C7 + cycles, on C1D8 and C1D15, and at discontinuation follow-up as per the study plan ([Appendix B](#)).

Subjects will undergo a 12-lead ECG after resting in a semi-supine position for at least 10 minutes prior to the scheduled test time. All ECGs should be performed in the same body position of the patient. Three ECGs will be performed at intervals of no more than 10 minutes during each ECG. Standardized ECG machines should be used and, if possible, patients should

be tested using the same machine throughout the study. ECGs may be performed in the event of any cardiac-related AE.

Each ECG result will be reviewed by the investigator or designated physician after ECG recordings are available. If an abnormal ECG is found at screening and is clinically significant judged by the investigator, it should be recorded in the medical history. For all ECGs, the rhythm, ECG intervals, and details of the overall assessment will be recorded, including heart rate, PR, R-R, QRS, and corrected QT interval (QTcF), etc.

Abnormal ECG findings that are clinically significant during treatment should be recorded as AEs in the eCRF. If the assessment is abnormal at discontinuation of treatment, reversibility of the abnormality should be assessed during the 28-day safety follow-up.

10.1.12 Echocardiography

Echocardiography will be performed to assess the patient's LVEF every 12 weeks from the first dose of the investigational product as per the study plan ([Appendix B](#)).

One subject should be examined using the same machine and operator whenever possible during the course of the study.

10.1.13 Ophthalmological Examination

Full ophthalmological examination will be performed at screening as per the study plan ([Appendix B](#)), including best corrected visual acuity, intraocular pressure, fundus examination, and slit lamp examination; the investigator or specialist will decide which items should be performed depending on the subject's condition, if clinically indicated during the course of the study. If a patient experiences any visual symptoms (including hazy vision) or abnormal eye symptoms and signs, an ophthalmic examination should be performed within 48 hours. Any clinically significant findings and symptoms, including those confirmed by the ophthalmologist, must be reported as adverse events. Ophthalmological examination results should be recorded in the eCRF. Patients with corneal ulcers will no longer be allowed to resume the study treatment. Any clinically significant ophthalmological findings should be photographed for documentation. If necessary, these photographs should be provided to the Sponsor for central review.

10.2 Efficacy Evaluation

10.2.1 Response Evaluation in Solid Tumors as per RECIST 1.1

RECIST 1.1 will be used to assess each subject's response to anti-tumor therapy and to calculate PFS, ORR, DoR, DCR, and DepOR at the time of tumor assessments performed by the investigator. The standard definitions for measurable lesions, non-measurable lesions, TLs,

NTLs, complete response (CR), partial response (PR), stable disease (SD), and disease progression (PD), etc. specified by RECIST 1.1 are provided in [Appendix D](#). The analysis of the primary endpoint in this study will be based on the investigator's assessment of tumor response per RECIST 1.1, and the management of subjects by the investigator will only be performed based on the results of this assessment.

Baseline CT or MRI assessments of chest, abdomen, and brain tissue must be performed within 28 days prior to the start of study treatment (regardless of the time of signing the ICF), and it should be performed as close as possible to the start of study treatment. The investigator should perform additional imaging examinations based on the signs and/or symptoms of each subject. The same method as the baseline assessment (CT/MRI) should be used at each subsequent follow-up assessment. Brain metastases will be assessed as non-target lesions. If brain lesions are found at screening, a brain tumor assessment should be performed at each subsequent follow-up; for patients without brain metastases at baseline, brain metastasis assessments are not necessary at subsequent follow-up, whichever is necessary assessed by the investigator.

During the randomized treatment period, tumor response will be assessed every 6 weeks (\pm 1 week; C1 to C21) or every 12 weeks (\pm 1 week; C23 and thereafter) after randomization until disease progression as assessed by the investigator per RECIST 1.1. Tumor assessments should be performed as per the study plan whenever possible. If the assessment exceeds the scheduled timeframe (\pm 1 week) and the subject does not have disease progression, every effort should be made to perform subsequent assessments at the previously scheduled visit times while continuing study treatment. If a tumor is suspected at any other site, appropriate imaging examinations should also be performed at the suspected site.

When progression of non-target lesions occurs, the following criteria must be met: the overall worsening of non-target lesions has reached to the extent that treatment must be discontinued, even if the target lesion has achieved SD or PR. A modest increase in the size of one or more non-target lesions is usually not sufficient to qualify for unequivocal progression status. Therefore, it is less likely to determine the overall progression solely on the basis of change in non-target lesion in the presence of SD or PR of target lesion.

At each visit, the assessment of objective tumor response will be categorized as CR, PR, SD, and PD as per RECIST 1.1. During the assessment of progression of target lesions, the lesions should be compared with the smallest lesion throughout the course of treatment, and the lesions will be considered as PD if the magnitude of the increase meets the criteria. In the absence of disease progression, the lesion will be assessed as tumor response (CR and PR) and stable

disease (SD) by comparing with the lesions at baseline.

10.2.2 Central Review

All imaging data collected during the study, including tests performed during unscheduled visits, should be assessed with an independent central review (ICR) by a qualified Independent Review Committee (IRC) in accordance with the Imaging Independent Review Charter. The results of this independent assessment by the IRC will not be returned to the investigator.

10.2.3 Assessment of Progression After Administration of Donated Drug

After the first objective progression, subjects who continue to receive the original study treatment (donated drug) after disease progression may undergo tumor assessments every 6 weeks to obtain data on disease progression after the dosing of donated drug. RECIST 1.1 is recommended for the assessment of secondary progression in subjects. Central reviewing is not required for imaging results obtained during this period. The date of the secondary progression and the Investigator's assessment of progression status (progressed or not) at each assessment should be recorded in the eCRF.

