		1	2	3	4	5	6	7-9		28-day follow-up ^b	Progression Follow-up Every 6/12 weeks	Survival Follow-up Every 6 weeks
Treatment cycle ^{c/day}		C1 D1	C1 D8	C1 D15	C2 D1	C3 D1	C4-C6 D1	D1 of C7 and Every 6/12 weeks thereafter	NA	NA	NA	NA
Day	-28	1	8	15	22	43	64-106	127+	NA	NA	NA	NA
Window period (days)	NA	0	±2	±2	±2	±7	±7	±7	+7	NA	±7	±7
Comments	
a. Subjects will be followed every 3 weeks (1 cycle) from Cycles 1 to 6; every 6 weeks (2 cycles) from Cycle 7 onwards; and two additional visits will be added on C1D8 and C1D15.
 
b. Subjects should be followed up by telephone 28 days (± 7 days) after discontinuation of study drug.
 
c. One cycle is defined as 21 days of continuous treatment.
 
d. These assessments at baseline should be completed prior to dosing on the visit day. If screening tests are completed within 7 days prior to the first dose of investigational product, they will not be required to perform on C1D1.
 
e. ECGs may be performed in the event of any cardiac-related AE.
 
f. Baseline tests should be performed within 28 days prior to the first dose. Assessments will be performed every 6 weeks after the start of treatment until disease progression as determined by centralized assessment per RECIST 1.1 criteria, even if the subject discontinues treatment prior to progression or has received other anti-tumor therapies. Tumor assessment data will be obtained from CT or MRI (contrast-enhanced CT or MRI is recommended to be preferred).
 
g. Tumor response results assessed by the investigator will be collected.
 
h. Subjects should be contacted to determine their survival status after the data cutoff date as determined by OS analysis.
											

• Study Plan for HS-10296 Crossover Treatment												
Visit ^a	HS-10296 Pre-crossover Visit	Treatment Period							Study Discontinuation Follow-up	Follow-up Period		
		2	3	4	5	6	7-9	10+		28-Day Follow-up	Progression Follow-up Every 6 weeks	Survival Follow-up Every 6 weeks
Treatment cycle ^b	C0	C1	C1	C1	C2	C3	C4-C6	Every 6 weeks from C7 onwards	NA	NA	NA	NA
Day	-28	D1	D8	D15	D22	D43	D64-106	D127	NA	NA	NA	NA
Window period (days)	NA	0	±2	±2	±2	±7	±7	±7	+7	NA	±7	±7
Informed consent	×											
Collection of tumor/blood samples after disease progression during the randomized treatment phase	×											
T790M mutation test	×											
Tumor assessment	×	The assessment is recommended to perform every 6 weeks ± 7 days per RECIST 1.1									×	

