#### 4.2. Sensitivity Analysis of the Primary Efficacy Endpoint

The following sensitivity analysis is performed on the primary efficacy endpoint:

- Considering the presence of primary resistance to EGFR TKI in non-small cell lung cancer patients with sensitive EGFR mutations, the early progression data may not satisfy the statistical assumptions of proportional hazards. The primary event censoring rules will be adopted to analyze the data of patients with primary drug resistance removed from the primary efficacy endpoint (progression within 3 months) in the full analysis set
  - The primary event censoring rules are used for analysis of the main efficacy endpoint in the per-protocol set
    - The primary event censoring rules are used for analysis of the main efficacy endpoint minus 42 days of patients with disease progression after 15 months in the full analysis set
    - The primary event censoring rules are used for re-analysis of the main efficacy endpoint based on the full analysis set
  - The primary event censoring rules are used for analysis of the PFS results derived by IRC evaluation based on the full analysis set
  - Based on the primary event censoring rules, subjects for whom the main efficacy endpoint is evaluated as "NE" before progression because of the epidemic are censored to the date on which the evaluation result before disease progression is "NE" for sensitivity analysis

Table 4.2-1PFS event censoring rules 2 (secondary event censoring rules)

Situation	Date	Outcome
No baseline or post-baseline imaging evaluation results	Date of randomization	Censored

No progression before data cutoff	Date of the last valid imaging examination before data cutoff	Censored
Progression or death before data cutoff	Examination date of first imaging disease progression or date of death	Progression or death

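### IRC-assessed PFS is run only under censoring rules that treat an unconfirmed investigator progression as non-informative, and the protocol does not settle which later scans are taken and read centrally

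*Protocol*

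**What the plan says.** **What is read centrally.** Protocol 10.2.2 states: "All imaging data collected during the study, including tests performed during unscheduled visits, should be assessed with an independent central review". Protocol 12.1.2 and SAP 1.2.8 repeat this without exception. Section 10.2.3 concerns a subset: "subjects who continue to receive the original study treatment (donated drug) after disease progression may undergo tumor assessments every 6 weeks". For their scans it says: "Central reviewing is not required for imaging results obtained during this period". Neither section refers to the other.

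**When scanning ends.** Under Protocol 10.2.1, tumor assessments run "after randomization until disease progression as assessed by the investigator per RECIST 1.1". Under Appendix B, footnote f, they run "until disease progression as determined by centralized assessment per RECIST 1.1 criteria". Section 10.1.1 has gefitinib patients sign the crossover consent after central review has confirmed progression, yet 10.2.2 says: "The results of this independent assessment by the IRC will not be returned to the investigator".

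**How IRC PFS is analysed.** SAP 4.2 says: "The primary event censoring rules are used for analysis of the PFS results derived by IRC evaluation based on the full analysis set". Those rules (Table 4.1-2) censor a patient without an event at the last valid imaging before data cutoff. If treatment stopped or new systemic therapy began without imaging progression, they censor at the last valid imaging before that point. Protocol 12.3.2 and SAP 1.2.8 give IRC results a sensitivity role only.

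**The concern.** An investigator's call of progression normally ends scheduled scanning, and usually ends treatment. If the IRC does not agree, the patient leaves the IRC risk set at about that scan. Such patients are likely to be nearer to IRC progression than those still under observation, so the censoring is informative.

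IRC PFS is there to test whether the investigator-assessed result depends on the assessor. An investigator's call also opens the way to unblinding (Protocol 7.6.1) and, on gefitinib, to crossover (9.2). The check is therefore weakest for the patients on whom the two assessors disagree. No planned output repairs this. In SAP section 7, the overall IRC analysis (14.2.5) uses the primary rules, the other IRC figures are Kaplan-Meier curves by mutation type and brain metastasis, the secondary rules (14.2.4) are applied to investigator PFS only, and no table compares the two assessors by arm.

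**Working it through.** **1. The plan's own figure.** Inputs from Protocol 5.3: HR 0.67 (medians 10 and 15 months), two-sided alpha 0.05, power 90%, 1:1 allocation, 8 months' accrual, 23 months' maximum observation, 262 events, about 410 patients.

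- Schoenfeld: 4 × (1.960 + 1.282)² / (ln 0.67)² = 4 × 10.51 / 0.1604 = 262.1. Power at 262 events is 0.8999.
- Event probability with exponential PFS and uniform accrual: 1 − [exp(−15λ) − exp(−23λ)] / (8λ), with λ = ln 2 / median. This gives 0.729 and 0.582, mean 0.655, so N = 262 / 0.655 = 400, close to 410.

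These figures belong to investigator PFS and are not in question. The 262 are PFS events, deaths included, so they are not a count of progressions.

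**2. What happens after an unconfirmed call.**

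- *Patient stops study drug.* Under 10.2.1 there is usually no later scheduled scan. Table 4.1-2 censors at the last valid scan before treatment ended or new therapy began. Deleting 10.2.3 changes nothing here.
- *Patient stays on the assigned drug.* Later scans are recommended (9.1.3.3) or may be done (10.2.3). If they are not read centrally, the patient is censored at the last centrally read scan. This is the only group that 10.2.3 affects.
- *If Appendix B footnote f governed*, scans would run to central progression and much of the problem would go. The documents do not say which text governs.

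**3. Size, under assumptions.** The documents give neither a discordance rate nor a rate of continuing on drug. The simulation used 300 trials of 410 patients per scenario, with the 5.3 inputs and scans every 6 weeks to week 60, then every 12 weeks. It assumed that IRC progression lags an unconfirmed call by a mean of 3 months and that 30% of patients stay on drug. There are about 257 investigator progressions per trial. Three versions of IRC PFS are compared: nothing read after the investigator's call; donated-drug scans read; everyone scanned and read to IRC progression.

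Equal discordance:

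| Unconfirmed, each arm | Patients (on donated drug) | IRC events: none / donated / all read | HR: none / all | Medians in months (gefitinib/HS-10296): none | Medians: all |
|---|---|---|---|---|---|
| 10% | 26 (8) | 231 / 238 / 253 | 0.685 / 0.684 | 12.0/18.0 | 11.2/16.8 |
| 20% | 52 (16) | 206 / 219 / 249 | 0.665 / 0.667 | 13.5/19.7 | 11.5/17.5 |
| 30% | 77 (23) | 180 / 200 / 245 | 0.675 / 0.677 | 15.8/20.9 | 12.0/17.9 |

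Reading the donated-drug scans recovers 238 − 231 = 7, 219 − 206 = 13 and 200 − 180 = 20 events, of 22, 43 and 65 lost. At 30% discordance, with 10% or 50% staying on drug, it recovers 186 − 180 = 6 or 213 − 180 = 33.

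Unequal discordance:

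| Gefitinib / HS-10296 | HR: none / donated / all read | Shift | Recovered by donated-drug reads |
|---|---|---|---|
| 30% / 15% | 0.826 / 0.786 / 0.723 | 0.826 − 0.723 = 0.103 | 0.826 − 0.786 = 0.040 |
| 15% / 30% | 0.561 / 0.590 / 0.648 | 0.648 − 0.561 = 0.087 | 0.590 − 0.561 = 0.029 |

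At 20% / 10% the HR is 0.74 with nothing read and 0.72 with donated-drug scans read, a recovery of about 0.02 (0.01 to 0.03 for 10 to 50% staying on drug).

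**4. Closed-form check.** If unconfirmed calls never become IRC events, the IRC hazard scales by (1 − q), where q is the unconfirmed share, and the HR reads 0.667 × (1 − q on HS-10296) / (1 − q on gefitinib). For 30% / 15% this is 0.667 × 0.85 / 0.70 = 0.81; reversed, 0.667 × 0.70 / 0.85 = 0.55. Both are close to the simulated 0.83 and 0.56.

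The simulation has no deaths, no dropout and no IRC progression earlier than the investigator's.

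**The case against.** The strongest case against runs as follows.

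- *Section 10.2.3 can be read as a specific exception to 10.2.2.* It leaves reading optional and concerns secondary progression, and 10.2.2 defers to an imaging charter that is not among the documents. This is fair, but no text calls it an exception, and optional reading lets practice vary between patients.
- *Only a sensitivity analysis is affected.* This stands in full.
- *Nothing shows that discordance differs by arm.* This also stands. Calls are made blinded under double dummy (6.2, 7.5), unblinding follows data cleaning (7.6.1), and crossover needs a positive T790M test (9.2.1.4). Against that, the decision to stay on drug may be made after unblinding (6.1) and only gefitinib patients can cross over. Which patients have later scans could therefore differ by arm.
- *A later death may count as an IRC event under Table 4.1-2.* This is true unless treatment had ended or two or more consecutive visits were missed, so the event losses above are on the high side.
- *Both assessors' results are already listed by subject* (Lists 16.2.5.1, 16.2.5.2, 16.2.6.1 and 16.2.6.2). They are, but listings do not summarise discordance by arm.
- *Counting the investigator's call as an event brings back the assessor being checked.* This is correct, so such an analysis can only supplement the IRC analysis.

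A reader might infer that 10.2.3 itself causes the informative censoring, or that the IRC hazard ratio is biased. The documents support neither. 10.2.3 covers only patients who stay on drug, and the hazard ratio moves only if discordance differs by arm.

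**Conclusion.** The point holds as a weakness of the independent check. IRC PFS has a single set of censoring rules, and under them an unconfirmed investigator progression leads to informative censoring. The main causes are that scanning stops at investigator progression and that Table 4.1-2 censors at treatment end or new therapy. Section 10.2.3 is a lesser contributor and a textual conflict.

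The size rests on assumed discordance of 10 to 30%, a mean lag of 3 months and 30% staying on drug. Equal discordance leaves the IRC hazard ratio almost unchanged but lengthens medians; at 30% they read 15.8 and 20.9 months against 12.0 and 17.9 with full reading. Discordance of 30% against 15% shifts the hazard ratio by about 0.1 in either direction, of which reading donated-drug scans recovers 0.03 to 0.04. The primary test, its alpha and its power do not change. The matter is worth fixing because the remedy is cheap, but it is not a threat to the primary result.

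**What to change.** **SAP 4.2 and section 7.** Add one supplementary IRC PFS analysis in which a patient without IRC progression, but with an investigator progression, counts as an event at the investigator's date. Read it with the planned IRC analysis as two ends of a range. Add a table of investigator/IRC agreement by arm: both progressed, investigator only, IRC only, neither, and differences in date. Both cover all affected patients, whether or not they stayed on drug.

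**Protocol.** Reconcile 10.2.2, 12.1.2 and SAP 1.2.8 with 10.2.3. Reconcile 10.2.1 with Appendix B footnote f, and 10.1.1 with the rule in 10.2.2 that IRC results are not fed back. The text should say which post-progression scans are taken and which of them the IRC reads. How long patients are scanned is for the sponsor to decide; the passages must agree.

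**Cost.** One extra analysis, one table and possibly central reads of scans already taken. The supplementary analysis leans partly on investigator calls, so it serves as a bound and does not replace the IRC analysis.
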